17.1.3. AZD7442 NASAL FLUID CONCENTRATIONS

Individual AZD7442 (AZD8895 and AZD1061) nasal fluid concentration data will be listed and tabulated by mAb component, along with descriptive statistics for the participants in the PK analysis set who have at least one quantifiable nasal fluid PK observation post-dose.

17.1.4. NEUTRALIZING ANTIBODY GEOMETRIC MEAN TITERS AND GEOMETRIC MEAN FOLD RISE

Geometric mean titers (GMTs) and geometric mean fold rises (GMFRs) for nAbs will be calculated for the active and control groups and will be summarized at each scheduled visit as per protocol section 1.3. GMT and GMFR summaries will be based on the nAb evaluable analysis set.

Descriptive statistics for GMTs and GMFRs will include number of participants, geometric mean, geometric standard deviation (GSD), 95% CI, minimum and maximum.

The GMT will be calculated as the antilogarithm of $\Sigma(\log_2 \text{ transformed titer/n})$, i.e. as the antilogarithm transformation of the mean of the log-transformed titer, where n is the number of participants with titer information. The GSD for GMT will be calculated as the antilogarithm transformation of the standard deviation of the log-transformed titer. The 95% CI will be calculated as the anti-logarithm transformation of the upper and lower limits for a two-sided CI for the mean of the log-transformed titers.

The fold rise is calculated as the ratio of the post-dose titer level to the pre-dose titer level. GMFR will be calculated as anti-logarithm of Σ (log₂ transformed (post-dose titer/ pre-dose titer)/n). The GSD and 95% CIs for GMFR will be calculated similarly to those for GMT.

All nAb data will be listed.

17.1.5. MISSING DATA IMPUTATION METHOD FOR PK, PD, AND ADA ENDPOINTS

The PK descriptive analyses of serum AZD7442 concentrations (Section 17.1.1) and AZD7442 nasal fluid concentrations (Section 17.1.3) will use the following imputation methods: Individual concentrations below the LLOQ of the bioanalytical assay will be reported as Not Quantifiable (NQ) in the listings with the LLOQ defined in the footnotes of the relevant tables, figures, and listings (TFLs). Individual plasma concentrations that are Not Reportable (NR) will be reported as NR and those that are missing will be reported as No Sample (NS) in the listings. Plasma concentrations that are NQ, NR, or NS will be handled as follows for the provision of descriptive

statistics:

- Any values reported as NR or NS will be excluded from the summary tables and corresponding figures.
- At a time point where less than or equal to 50% of the concentration values are NQ, all NQ values will be set to the LLOQ, and all descriptive statistics will be calculated accordingly.
- At a time point where more than 50% (but not all) of the values are NQ, the geometric mean, geometric mean ± GSD and geometric coefficient of variation (gCV%) will be set to Not Computed (NC). The maximum value will be reported from the individual data, and the minimum and median will be set to NQ.
- If all concentrations are NQ at a time point, no descriptive statistics will be calculated for that time point. The geometric mean, minimum, median, and maximum will be reported as NQ and the gCV% and geometric mean ± GSD as NC.
- The number of values below LLOQ (n < LLOQ) will be reported for each time point together with the total number of collected values (n).

Three observations > LLOQ are required as a minimum for a plasma concentration or PK parameter (e.g. Cmax, Cmin, Clast) to be summarized. Two observations > LLOQ are presented as minimum and maximum with the other summary statistics as NC.

The analysis for the incidence of ADA to AZD7442 in serum (Section 17.1.2) will use the following imputation method: ADA titers values below the limit of detection (LOD) are negative results, hence they are not imputed and are excluded from calculation of summary statistics. Titer values of positive ADA samples reported as \leq LOD are imputed as LOD in the calculation of summary statistics on ADA titer.

The analysis of neutralizing antibody geometric mean titers and geometric mean fold rise (Section 17.1.4) will use the following imputation method: a titer value measured below the LLOQ will be imputed to a value that is half of the LLOQ in summaries and analyses, but will be listed as reported in the raw data. Titer values measured as above the upper limit of quantification (ULOQ) will be imputed at the ULOQ value.

17.1.6. SENSITIVITY ANALYSES FOR PK, PD, AND ADA ENDPOINTS

No sensitivity analysis will be performed for the PK, PD, and ADA endpoints.

17.1.7. SUPPLEMENTARY ANALYSES FOR PK, PD, AND ADA ENDPOINTS

No supportive analysis will be performed for the PK, PD, and ADA endpoints.

18. SAFETY ENDPOINTS

The safety of AZD7442 will primarily be assessed by:

- Incidence of AEs
- Incidence of SAEs
- Incidence of medically attended adverse events (MAAEs, defined in Protocol Section 8.3.5)
- Incidence of adverse events of special interest (AESIs, defined in Protocol Section 8.3.4)

There are also other safety endpoints, including:

- Deaths
- Laboratory evaluations
- Vital signs
- ECG evaluations
- Physical examinations

All safety summaries will be presented by actual treatment group based on the SAF and may be summarized by cohort and/or comorbidities. Additional summaries may be presented by whether participants receive COVID-19 vaccination or other COVID-19 preventive product (Yes/No) during study and unblinding status (Yes/No) during study. Data will be presented using all the available data up to 15 months (Day 457) following the dose of IMP to the last assessment unless stated otherwise. There will be no statistical comparisons between the treatment groups for safety data.

18.1. ADVERSE EVENTS

All AEs will be coded using the MedDRA dictionary, version 23.1 or higher.

Unless specified, event summary refers to the summary of number of participants with the corresponding adverse event.

Overall summaries of number and percentage of participants with AE in the following categories will be provided by treatment group based on the SAF.

- AEs
- SAEs
- Related SAEs
- AEs leading to IMP discontinuation
- Related AEs leading to IMP discontinuation
- AEs leading to study discontinuation

- Related AEs leading to study discontinuation
- MAAEs
- Related MAAEs
- AEs with outcome of death
- AESIs
- Related AESIs

Should a participant experience multiple events within a category, the participant will be counted only once for that category.

An overall summary of number and percentage of participants, including exposure adjusted rates, and number of events within categories of all SAEs, related SAEs, AEs leading to study discontinuation, related AEs leading to study discontinuation, MAAEs, AEs with outcome of death, and AESIs during the entire period of study will be provided by actual treatment group. Exposure adjusted rate is calculated as number of participants with AEs in categories above divided by total participant-year exposure to investigational study intervention. Participant years is determined by summing the total number of follow-up days of each participant, and then dividing by 365.25. The exposure period is calculated from time of dose to end of study.

An overall summary of number of AEs within each of the categories will also be provided by actual treatment group.

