At 6 months (SS-D183), a subset of participants from USA sites in Group 1 and Group 2 who consent to receive additional AZD7442 600 mg doses (approximately evenly distributed between groups) approximately every 6 months and will be assigned to a new arm - Group 3. All other participants will continue in the sub-study according to their originally assigned dosing interval group schedule. The addition of Group 3 will create 4 possible dosing cohorts, based on the how many doses of 300mg AZD7442 received prior to entering Group 3 and whether or not this was followed by a further two doses of 600mg AZD7442:

Group 1

Cohort 1: AZD7442 300 mg, 300 mg

Group 2

Cohort 2: Placebo, AZD7442 300mg, 300 mg

Group 3

- Cohort 3 (from Group 1): AZD7442 300 mg, 300 mg, 600 mg, 600 mg
- Cohort 4 (From Group 2): Placebo, AZD7442 300 mg, 600 mg, 600 mg

Group level recruitment caps may be placed to ensure 50 or more participants complete the study with their assigned dose and valid samples.

Group 1 and Group 2 will undergo safety follow-up for 456 days after the last dose of AZD7442, and Group 3 will undergo safety follow-up for 183 days after the last dose of AZD7442. The total duration of the sub-study will be 457 days for Group 1, 639 days for Group 2, and 548 days for Group 3.

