9.4.1 Safety: Primary Endpoint

9.4.1.1 Primary Endpoint(s)

The safety of AZD7442 will primarily be assessed by:

- Incidence of AEs
- Incidence of SAEs
- Incidence of MAAEs
- Incidence of AESIs

The AE severity will be graded according to Appendix B and coded using the most recent version of the Medical Dictionary for Regulatory Activities. Adverse events will be presented for each dosing interval group by system organ class and preferred term. Summaries will include the number and percentage of participants reporting at least one event, number of events, and exposure adjusted rates, where appropriate.

An overview of AEs will be presented for each group, including the number and percentage of participants with any AE and SAEs. Summaries will present the relationship to IMP as assessed by the Investigator, maximum intensity, seriousness, and death.

A listing will cover details for each individual AE.

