- Stage 2 (N = 4850: 3233 to AZD7442, 1617 to placebo). Stage 2 will start only after an independent Data Safety Monitoring Board (DSMB) has confirmed it is appropriate to proceed. The DSMB will evaluate 7-day safety data from participants dosed in Stage 1. If hypersensitivity reactions are observed during Stage 1, safety monitoring for 2 hours post IMP administration will be implemented for Stage 2; otherwise the minimum safety monitoring time will be 1 hour.

To allow for the assessment of clonal material, 150 participants in the US will receive the clonal material or placebo in a 2:1 ratio. The participants will be recruited according to the current inclusion and exclusion criteria and will be followed as per the schedule of activities. A PK analysis will be performed of pooled versus clonal material.

Following a screening period of \leq 7 days, participants will receive a single dose (× 2 IM injections) of IMP. After administration of the dose of IMP on Day 1, participants will undergo follow-up for 15 months (until Day 457).

Figure A: Study Design

Following screening (-7 to 0 days), randomization will occur in 2 stages and is contingent on safety. The planned primary analysis will occur after approximately 24 primary endpoint events have occurred or 30% of study participants have become unblinded, whichever occurs first. A final analysis is planned when all participants complete the study (Day 457).

DSMB, Data Safety Monitoring Board

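### The SAP's exposure-adjusted rate keeps counting follow-up after a participant's first event, so it is not an incidence rate and falls as follow-up lengthens; this matters for common event categories

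*SAP*

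**What the plan says.** SAP 18.1 gives the numerator and the division: "Exposure adjusted rate is calculated as number of participants with AEs in categories above divided by total participant-year exposure". The counting rule for the overall summaries in that section is "Should a participant experience multiple events within a category, the participant will be counted only once for that category". The denominator is built from all follow-up: "Participant years is determined by summing the total number of follow-up days of each participant, and then dividing by 365.25", and "The exposure period is calculated from time of dose to end of study". Nothing stops a participant's time at the first event.

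The categories given this rate are all SAEs, related SAEs, AEs leading to study discontinuation (all and related), MAAEs, AEs with outcome of death, and AESIs. Any AE is not on that list.

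The SAP covers the parent study, where both arms receive one dose and are followed to Day 457 (SAP 3.1). The sub-study has its own plan in the protocol. Protocol 9.4.1.1 presents adverse events by dosing interval group with "number of events, and exposure adjusted rates, where appropriate", but defines no rate. Follow-up there differs by design (Protocol 4.1): "The total duration of the sub-study will be 457 days for Group 1, 639 days for Group 2, and 548 days for Group 3". No sub-study SAP was supplied.

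**The concern.** A participant-level incidence rate divides first events by time at risk of a first event. An event rate divides all events by all person-time. The SAP formula takes its numerator from the first and its denominator from the second. The numerator can grow no further once a participant has had an event, while that participant's days keep accruing. At a fixed hazard the figure therefore falls as follow-up lengthens.

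The purpose of an exposure adjustment is to make groups with unequal observation time comparable. This one does so only approximately, and worst where events are common. In the parent study it can understate a relative difference between arms. If carried into the sub-study, it can create a difference between groups that have the same hazard.

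**Working it through.** **Plan's own figure.** The documents state no numerical exposure-adjusted rate, so there is none to reproduce.

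**Inputs.** Follow-up of 457 days in the parent study (SAP 3.1) and 457, 639 and 548 days for sub-study Groups 1, 2 and 3 (Protocol 4.1). For time from the repeat dose: 456 days after the last dose for Groups 1 and 2 (639 − 183 = 456 for Group 2), and 548 − 183 = 365 days for Group 3 from its first 600 mg dose at SS-D183. A year is 365.25 days (SAP 18.1). No event rates are given, so cumulative incidence by Day 457, c, is assumed at 5%, 30% and 50%.

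**Formulas.** Assume a constant hazard h and complete follow-up for T years.
- Hazard: h = −ln(1 − c) / (457/365.25). This gives 4.10, 28.51 and 55.40 per 100 person-years.
- SAP rate: (1 − exp(−hT)) / T, which falls as T grows for any h > 0.
- Rate with time stopped at the first event: (1 − exp(−hT)) divided by (1 − exp(−hT))/h, which is h for every T.

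**Parent study, equal follow-up.** T cancels, so the ratio of SAP rates is the risk ratio. For a true hazard ratio of 2 it is (1 − (1 − c)²)/c = 2 − c, with c the control-arm incidence: 1.95, 1.70 and 1.50. At equal hazards the ratio is 1.

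**Parent study, unequal actual follow-up (illustration).** If one arm or subgroup averaged 274 days against 457 (assumed), the ratio of the longer to the shorter at equal hazard would be 0.990 at c = 5% and 0.882 at c = 50%.

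**Sub-study, if the formula is carried over and time runs from SS-D1.** SAP rate per 100 person-years at the same hazard:

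| Assumed incidence by Day 457 | 457 days | 548 days | 639 days | Ratio 639 to 457 | Rate stopped at first event |
|---|---|---|---|---|---|
| 5% | 4.00 | 3.98 | 3.96 | 0.990 | 4.10 at all three |
| 30% | 23.98 | 23.19 | 22.45 | 0.936 | 28.51 at all three |
| 50% | 39.96 | 37.62 | 35.47 | 0.888 | 55.40 at all three |

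A simulation with 2,000,000 participants per cell agrees. At 50% incidence the SAP rate was 39.95 at 457 days and 35.49 at 639 days, and the rate stopped at first event was 55.38 and 55.44.

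**Sub-study, if time runs from the repeat dose.** Groups 1 and 2 both have T = 456 days, so the artefact between them vanishes. Group 3 at 365 days from SS-D183, compared with 456 days, gives 4.02 against 4.00, 24.81 against 23.99, and 42.54 against 39.99. Group 3 would therefore read higher by factors of 1.005, 1.034 and 1.064 at the same hazard.

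**The case against.** The strongest objection concerns scope. The formula belongs to the parent-study SAP, whose arms share planned follow-up. The sub-study protocol gives no formula, and the supplied SAP is plainly written for a single dose: its clock starts at the dose, which is undefined when there are several. This stands, so the sub-study effect is conditional.

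A reader might infer that the plan will make Group 2 look about 17% safer than Group 1. That figure arises at a hazard of 1 per year with 638 against 456 days (0.47 against 0.57 per year). The documents do not support it, for three reasons:
- The primary endpoint is events after the repeat dose (Protocol 3), and both groups are followed for 456 days after the last dose. The gap disappears if exposure starts there.
- A hazard of 1 per year means about 71% of participants affected by Day 457 (1 − exp(−457/365.25)), and no document gives such an incidence for any listed category.
- Any AE, the category most likely to be that common, is not on the SAP's list for this rate. It enters only if the sub-study chooses to report it.

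It is also fair to say that safety is descriptive. The SAP states "There will be no statistical comparisons between the treatment groups for safety data", Protocol 9.1 tests no hypotheses, and percentages and event counts appear beside the rate. No test or sample size is affected. That limits the consequence, but it does not make the stated formula an incidence rate.

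Finally, stopping time at the first event restores comparability only under a roughly constant hazard. This is correct, and the fix allows for it.

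**Conclusion.** The formula should be corrected, as a modest point. As written, it is not an incidence rate and it declines with follow-up.

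In the parent study it creates no false difference at equal hazards unless actual follow-up differs between arms or subgroups. It does pull the rate ratio back to the risk ratio, which is slight at 5% control incidence and substantial at 50% (2 becomes 1.50).

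In the sub-study the effect depends on the formula being carried over and on where exposure starts. From SS-D1, Group 2 would read about 1%, 6% or 11% below Group 1 at assumed incidences of 5%, 30% or 50%. From the repeat dose, Groups 1 and 2 agree, and Group 3 would read about 0.5%, 3% or 6% above them.

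The effect is material only for common categories such as MAAEs, and any AE if the sub-study reports a rate for it. It is negligible for rare events. It is also negligible for deaths and AEs leading to study discontinuation, where little or no follow-up comes after the event. The sizes rest on a constant hazard, complete planned follow-up and assumed incidences.

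**What to change.** In SAP 18.1, define the participant-level rate as participants with at least one event in the category, divided by the sum of each participant's time from dose to the first such event or to end of follow-up, whichever is earlier. If wanted, add a separate event rate: all events divided by all person-years.

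Use the same definitions in the sub-study analysis plan. State there, for each group and cohort, when exposure starts (SS-D1, the repeat dose, or entry to Group 3) and when it ends.

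For events clustered after dosing, such as injection site reactions, report incidence in a fixed window after each dose, because long follow-up would still dilute a time-at-risk rate.

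The cost is a few sentences of SAP text and one derived time-to-first-event variable per category, from dates already collected. The remaining limitation is that the corrected rate is comparable across follow-up lengths only if the hazard is roughly constant, and the output should say so.

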18.1.1. ADVERSE EVENTS AND SERIOUS ADVERSE EVENTS

AEs will be recorded from the time of IMP administration throughout the study up to and including the last visit. Serious adverse events (SAEs) are those events recorded as "Serious" on the AE page of the eCRF. SAEs will be recorded from the time of signing of the informed consent form.

Adverse events and serious adverse events post the dose of IMP will be summarized by SOC and PT by actual treatment group. Specific AEs will be counted once for each participant for calculating percentages.

Summary of AEs and SAEs post the dose of IMP will be broken down further by maximum severity and relationship to study intervention. If the same AE occurs multiple times for a particular participant, the highest/worst severity (i.e. from highest to lowest: severe, moderate and mild) and level of relationship to study intervention observed will be reported.

Listings of AEs and SAEs will be provided. SAEs prior to the dose of IMP and AEs and SAEs starting after Day 457 will only be presented in the listings. For SAEs with partial dates, if the known part of the date indicates that SAE stopped before the dose of IMP, it will be considered as SAE prior to the dose of IMP. Otherwise, it will be considered as SAE post dose of IMP.

18.1.1.1. Severity for AEs

Severity will be classified as mild, moderate, severe, potentially life-threatening, or fatal (increasing severity) by using grading for AEs. Severity for AEs will be collected on "Adverse Events" form of the eCRF. Should a participant experience multiple events within a SOC or PT, only the participant's worst severity grade will be counted for that SOC or PT.

18.1.1.2. Relationship to IMP/Other Medication/Study Procedure

Relationship to IMP/other medication/study procedure, as indicated by the Investigator, will be classified as not related or related.

Should a participant experience multiple events within a SOC or PT, the participant will be counted as related for that SOC or PT if one of those is related.

18.1.2. AES LEADING TO DISCONTINUATION OF IMP

AEs leading to permanent discontinuation of IMP are not expected due to this being a single dose study. Given the single dose is comprised of 2 sequential injections, the AE would need to occur immediately after the 1st injection and lead to discontinuation of the 2nd injection—this scenario is expected to be rare. Therefore, no summary will be prepared.

A listing of all AEs leading to discontinuation of IMP will be provided, if data permit.

18.1.3. AES LEADING TO DISCONTINUATION OF STUDY

A summary of AEs during the study leading to permanent discontinuation of study by SOC and PT will be prepared. A summary of related AEs leading to permanent discontinuation of study by SOC and PT will also be prepared.

A listing of all AEs leading to permanent discontinuation of study will be provided.

18.1.4. AES WITH OUTCOME OF DEATH

AEs with outcome of death are those AEs with "Fatal" outcome recorded on the "Adverse Events" form of the eCRF. A summary of AEs with outcome of death by SOC and PT will be prepared. A summary of related AEs with outcome of death by SOC and PT will also be prepared.

18.1.5. MEDICALLY ATTENDED ADVERSE EVENTS

Medically attended adverse events (MAAEs) are AEs leading to medically-attended visits that were not routine visits for physical examination or dosing, such as an emergency room visit, or an otherwise unscheduled visit to or from medical personnel (medical doctor) for any reason. AEs, including abnormal vital signs, identified on a routine

study visit or during the scheduled Illness Visits will not be considered MAAEs. MAAEs will be recorded from Day 1, post dose, through the last participant contact.

A summary of MAAEs by SOC and PT by actual treatment group will be prepared. Should a participant experience multiple events within a SOC or PT, the participant will be counted only once for that SOC or PT. A summary of related MAAEs by SOC and PT will also be prepared.

A listing of all MAAEs will be provided.

18.1.6. ADVERSE EVENTS OF SPECIAL INTEREST

AEs of special interest (AESIs) are:

- Anaphylaxis and other serious hypersensitivity reactions including immune complex disease
- Injection site reactions

AESIs are indicated on the eCRF and will be recorded from Day 1, post dose, through the last participant contact. A summary of AESIs by SOC and PT by actual treatment group will be prepared. Should a participant experience multiple events within a SOC or PT, the participant will be counted only once for that SOC or PT. A summary of related AESIs by SOC and PT will also be prepared.

A listing of all AESIs will be provided.

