2.3.1 Risk Assessment

Based on all available clinical study data with a cut-off date of 20 August 2021, there were no identified risks associated with AZD7442. The current risk assessment for AZD7442 is summarized in Table 6.

Table 6 Risk Assessment for AZD7442

Important Identified Risks	None
Identified Risks	None
Important Potential Risks	None
Potential Risks	Potential risks include injection-related reactions, ADE disease, serious hypersensitivity including anaphylaxis, and cardiac and thromboembolic events.
Reference Safety Information	For AZD7442, no SARs have been identified. Any SAE that is deemed to be related to the IP by the Investigator or the Sponsor will be treated as a suspected unexpected serious adverse reaction and appropriately expedited.

Based on a data cut-off of 20 August 2021.

ADE, antibody-dependent enhancement of disease; IP, investigational product; SAE, serious adverse event; SAR, serious adverse reaction.

In the PROVENT parent study, AZD7442 was generally well tolerated and preliminary analyses showed that overall AEs were balanced between the placebo and AZD7442 groups. A small number of cardiovascular serious adverse events (myocardial infarction and cardiac failure) have been reported in the PROVENT parent study at a higher rate in participants who received AZD7442 compared to placebo. All participants who experienced cardiac SAEs were at high risk for cardiac events, many of whom had a prior history of cardiovascular disease at baseline. There was no clear temporal pattern and a causal relationship between AZD7442 and these events has not been established. There was no signal for cardiac toxicity or thrombotic events identified in the nonclinical studies. Monitoring of cardiovascular events will occur in this sub-study. There were no cases of severe COVID-19 or COVID-19-related deaths in those treated with AZD7442. In the placebo arm, there were 3 cases of severe COVID-19, which included 2 deaths.

In a separate Phase III AZD7442 study STORM CHASER (N = 1121), which enrolled a younger population with fewer baseline cardiac risk factors than PROVENT and no related cardiac SAEs at the time of primary analysis.

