8.3.4 Adverse Events of Special Interest

Adverse events of special interest will be collected according to the time points specified in the SoA (see Section 1.3).

Adverse events of special interest are events of scientific and medical interest, specific to the further understanding of the IMP safety profile, and require close monitoring and rapid communication by the Investigators to the Sponsor. An AESI can be serious or non-serious. All AESIs will be recorded in the eCRF. Serious AESIs will be recorded and reported as per Section 8.3.9. See also the AZD7442 IB, for additional information on AESIs.

AESIs for AZD7442 are listed below. They include:

- Anaphylaxis and other serious hypersensitivity reactions (Appendix E).
- Injection site reactions.
- Cardiac ischemia, cardiac failure, and thrombotic events.

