9.7.2 Cardiovascular Event Adjudication Committee

An independent Cardiovascular Event Adjudication Committee will provide an independent, external, systematic, and unbiased assessment of de-identified data to systematically evaluate cardiovascular events. The adjudicated cardiovascular events will be included in descriptive analyses of safety data. Further details of the Cardiovascular Event Adjudication Committee composition, operation, and listings of preferred terms to identify events are provided in a separate Cardiovascular Event Adjudication Committee Charter.

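### The parent-study SAP has no cardiac and thrombotic AESI class, whereas the later sub-study protocol lists one for AZD7442: the randomised data get no grouped rate by arm, and AESI totals do not match between single and repeat dosing

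*SAP*

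**What the plan says.** The two supplied documents belong to two linked studies. The SAP covers the randomised, placebo-controlled parent study and is written to parent protocol v9.0 of 26 July 2021. The supplied protocol is the later open-label repeat-dose sub-study.

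- **SAP 18.1.6** has two AESI classes. The first is "Anaphylaxis and other serious hypersensitivity reactions including immune complex disease"; the second is injection site reactions. Identification is by case report form: "AESIs are indicated on the eCRF and will be recorded from Day 1, post dose, through the last participant contact".
- **Sub-study protocol 8.3.4** opens its list with "AESIs for AZD7442 are listed below" and gives three classes: serious hypersensitivity (without naming immune complex disease), injection site reactions, and "Cardiac ischemia, cardiac failure, and thrombotic events".
- **Sub-study protocol 2.3.1** says that a small number of cardiovascular SAEs, myocardial infarction and cardiac failure, "have been reported in the PROVENT parent study at a higher rate in participants who received AZD7442 compared to placebo". It adds that no causal link has been established.
- **Sub-study protocol 9.7.2** sets up a cardiovascular adjudication committee and says that "listings of preferred terms to identify events are provided in a separate Cardiovascular Event Adjudication Committee Charter".
- **Both documents** make AESI incidence a primary safety measure (SAP 18; protocol 9.4.1.1). Protocol 4.2 asks whether the safety profile after a repeat dose is comparable to that after a single dose.

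**The concern.** The one event class with a reported imbalance between arms is not an AESI class in the plan that governs the randomised data. AESI status affects the output. SAP 18.1 gives exposure-adjusted rates only for named categories, and AESIs are one of them. A cardiac or thrombotic event outside that category counts toward overall SAE or MAAE figures and otherwise appears under its own SOC and PT. No line adds the group up by arm.

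The second effect falls on the comparison in protocol 4.2. A total over three classes in the sub-study cannot be read against a total over two in the parent study, because a difference between them could reflect the definitions alone.

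**Working it through.** The documents state no figure for this point, so the main check is of the text.

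**1. Definitions side by side**

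| Class | SAP 18.1.6 (parent) | Protocol 8.3.4 (sub-study) |
|---|---|---|
| Serious hypersensitivity | Yes, immune complex disease named | Yes, immune complex disease not named |
| Injection site reactions | Yes | Yes |
| Cardiac and thrombotic | No | Yes |

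That is two classes against three, with a second, smaller difference over immune complex disease.

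**2. Does another part of the SAP fill the gap?** SAP 4.2 adjudicates deaths for a COVID-19 cause only. Sections 18.1.1 to 18.1.5 tabulate AEs, SAEs, fatal AEs and MAAEs without a cardiac grouping. Appendix 3 lists no cardiac biomarkers. No section defines a cardiac or thrombotic group or a term list for one.

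**3. What is still reported.** Cardiac events appear by actual treatment group in the SOC and PT tables for AEs, SAEs and MAAEs, and in the fatal-event tables and listings. What is missing is the number and percentage of participants with any event in the group, and the exposure-adjusted rate, by arm.

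**4. Timing.** The SAP is dated 29 July 2021. The risk assessment in protocol 2.3.1 uses a cut-off of 20 August 2021, and protocol 4.3 refers to an authorisation of 24 February 2022. The SAP therefore came first. It also covers the final analysis after the last Day 457 visit (SAP 4.5).

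**5. How far the arms stay as randomised.** Sub-study entry is at 12 ± 2 months, which protocol Tables 2 and 3 express as Day 366 ± 61. That runs from 366 − 61 = Day 305 to 366 + 61 = Day 427. A parent placebo participant who joins can therefore receive AZD7442 between 457 − 427 = 30 and 457 − 305 = 152 days before the Day 457 horizon. SAP 18.1 counts exposure from dose to end of study, with no cut at that dose.

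**6. Which data can inform on the imbalance (illustration only).** The documents give no cardiac rates. Assume a placebo risk p of 0.2%, 0.5% or 1.0%, a relative risk of 2, and equal risk per participant in both studies. The parent arms are about 3433 and 1717 (SAP 3.1); the sub-study has about 500, all given AZD7442 (protocol 9.2).

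| Assumed p | Parent placebo, 1717 × p | Parent AZD7442, 3433 × 2p | Sub-study, 500 × 2p |
|---|---|---|---|
| 0.2% | 3.4 | 13.7 | 2.0 |
| 0.5% | 8.6 | 34.3 | 5.0 |
| 1.0% | 17.2 | 68.7 | 10.0 |

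Across this range the sub-study expects 2 to 10 events with no concurrent control. The parent study is the main source on the question.

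**The case against.** The strongest reply is that two different studies are being compared. When SAP 18 sends the reader to protocol section 8.3.4 for the AESI definition, it means parent protocol v9.0. The SAP may match that version exactly, and it was signed before the cut-off of the risk assessment that describes the imbalance. This stands. A reader might infer that the SAP breaks with its own protocol or ignored a known signal; the documents support neither. A later SAP version cannot be seen or ruled out.

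A reader might also infer that the cardiac events go unanalysed. They do not: they are tabulated by arm, and protocol 2.3.1 itself reports a comparison with placebo. The gap is the grouped summary.

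Nor is the Day 457 comparison the only randomised one, since the primary analysis uses the same arms. It is not free of confounding either, because placebo participants may by then have taken AZD7442 in the sub-study.

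It is tempting to say that repeat-dose AESI incidence must come out higher by a stated factor. With no rates in the documents, any factor would be invented. Even the direction is not certain, because immune complex disease is named only in the SAP.

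Two further points stand and shape the remedy. SAP AESIs are themselves summarised by SOC and PT, so adding a class name alone would not produce a grouped count. And because AESIs come from a case report form flag, cardiac events could enter the table if the form had allowed for them; the SAP text makes no provision for this.

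**Conclusion.** The concern holds as a difference between the parent SAP and the later sub-study protocol. If the SAP is followed as written, its AESI totals and exposure-adjusted AESI rates leave out the class with the reported imbalance, and they do not match the AESIs of the sub-study. The documents fix the size only as two classes against three; the effect on any rate cannot be computed from them. The conclusion assumes that SAP v4.0 still governs the final analysis and that the AESI flag in the parent study follows the SAP's list. This is an inexpensive improvement to a primary safety measure and does not invalidate the planned safety analysis.

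**What to change.** Before the Day 457 final analysis, amend SAP 18.1.6 as follows.

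- Add "Cardiac ischemia, cardiac failure, and thrombotic events" as a separate AESI class, identified by a prespecified preferred-term list. Start from the list in the cardiovascular adjudication charter and check that it covers thrombotic terms, since the charter is described as covering cardiovascular events.
- Report each AESI class separately by arm: participants with at least one event, percentage, and exposure-adjusted rate. Keep this descriptive. SAP 18 plans no statistical comparison of arms for safety, and none is needed here.
- State how immune complex disease is classed in both studies.
- Count time and events of parent placebo participants only up to their first AZD7442 dose in the sub-study. By the same reasoning, a rate described as single-dose should stop at the second dose for AZD7442 participants who join the sub-study.
- Use the same class definitions, tabulated separately, wherever sub-study AESIs are set beside single-dose AESIs.

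The cost is a SAP amendment and one more programmed term list on AE data already collected. The downside is that the class is added after the imbalance was seen, and the outputs should be labelled accordingly.
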